**NIDA CCTN Scientific Officer:**

**[name]**

## A. List of Abbreviations

| Abbreviation | Definition                           |
|--------------|--------------------------------------|
| BPA          | Best Practice Advisory               |
| CDS          | Clinical Decision Support            |
| CSSRS        | Columbia Suicide Severity Risk Scale |
| CTN          | Clinical Trials Network of NIDA      |
| DSMB         | Data Safety Monitoring Board         |
| ED           | Emergency Department                 |
| EHR          | Electronic health record             |
| IRB          | Institutional Review Board           |
| MHRN         | Mental Health Research Network       |
| NIDA         | National Institute on Drug Abuse     |
| NIH          | National Institutes of Health        |
| OUD          | Opioid use disorder                  |
| PCC          | Primary care clinician               |

## B. Summary

This study integrates the Mental Health Research Network (MHRN) suicide risk models into Opioid Wizard, an electronic health record (EHR) clinical decision support (CDS) to identify and treat patients at high risk of opioid use disorder (OUD)/overdose or diagnosed with OUD, to alert primary care clinicians (PCCs) to patients at elevated risk for suicide and guide them through structured suicide risk assessment. In both intervention and control clinics, suicide risk scores will be calculated for all Opioid Wizard-eligible patients and relevant EHR data to inform analyses will be archived. In intervention clinics, Opioid Wizard will alert PCCs to Opioid Wizard-eligible patients who are at increased risk of suicide and coach them through use of the Columbia Suicide Severity Risk Scale (CSSRS), a structured tool in the EHR that will help PCCs assess immediate suicide risk. Based on the resulting CSSRS score, Opioid Wizard will provide EHR links for risk-based referrals and follow-up recommendations, including care as usual, routine or emergent referral to behavioral health, or transportation to the emergency department (ED) for further assessment. Primary outcome measures include completion of CSSRS assessments for at-risk patients and patient engagement in outpatient mental health care.

## C. Background and Rationale

Two public health issues of paramount importance -- suicide and opioid overdose -- have substantial overlap. Depression and other mental health conditions increase the risk of both opioid use disorder (OUD) and suicide, and people with OUD are more likely to have depression and other mental health conditions. In fact, the risk of both suicide and opioid overdose is likely highest in those with both OUD and mental health diagnoses. More than 48,000 people died of suicide and 46,000 of an opioid overdose in the US in 2018, and over 40% of suicide and overdose deaths involved opioids. Ultimately, people with OUD are 13 times more likely to die by suicide than the general population.

OUD and opioid misuse are associated with suicidal ideation and suicide attempts, but distinguishing intentional and unintentional overdoses is complicated. The proportion of opioid-overdose deaths that are suicides is likely considerable and underestimated, as it is challenging to classify overdoses according to intent. Furthermore, intentionality of overdose is likely dimensional, rather than categorical, with many overdoses not fully intentional or unintentional.

Suicide deaths and overdose deaths share common risk factors, and while historically most overdoses have been thought to be unintentional, more recent evidence suggests that a significant proportion – estimated to be 20 to 30% - are intentional.

The US Preventative Services Task Force found insufficient evidence to support universal screening for suicide risk, but this is not to discourage screening at-risk populations, such as people with or at high risk for OUD or opioid overdose. A recent commentary in the New England Journal of Medicine states that improved screening for suicide risk along with rapid access to treatment is critical to prevent opioid-related suicide deaths in patients with OUD. Ultimately, people with OUD should be targeted for prevention of both suicide and opioid overdose, recognizing that mental health conditions in this population will further increase risk. To that end, this ancillary study, which will help primary care clinicians (PCCs) both identify people at risk for OUD/opioid overdose and a subset at increased risk of suicide, is particularly timely and important. In addition to guiding PCCs through structured assessment of suicide risk and providing decision support for recognition and treatment of depression, our study's potential to improve access to medications for OUD is also thought to reduce rates of intentional (and unintentional) overdose.

#### **D. Specific Aims & Hypotheses**

People with OUD are at increased risk of depression and other mental health conditions, and a significant proportion of opioid-related deaths are likely suicides. Yet systematic screening of patients with OUD for suicide risk is rarely done. Nearly 50% of patients who die by suicide make a healthcare visit in the prior month, most often to primary care. Primary care has an important role to play in suicide prevention.

In the NIMH-funded Mental Health Research Network (MHRN; 1U19MH121738), research team members developed and validated electronic health record (EHR)-based suicide risk prediction models that substantially outperform previous such tools. These validated suicide risk models were developing using machine learning with a large number of EHR and administrative database variables to estimate risk of suicide, with an area under the curves (AUC) of 0.83 to 0.86. The team is now updating this tool to add predictors specific to a population of people with OUD to the model, including prescription opioid use, opioid dose reduction, opioid discontinuation, and medications to treat OUD (R01DA047724). To date, this risk prediction tool has not been integrated into routine care processes in large healthcare delivery systems.

In the NIDA Clinical Trials Network-funded study [COMPUTE 2.0 \(CTN-0095\)](#), our research team has developed a clinical decision support (CDS) system that is integrated with the EHR and is designed to guide primary care clinicians (PCCs) in the identification, diagnosis and treatment of OUD. This non-proprietary tool, coined Opioid Wizard, uses a proven point-of-care CDS platform to guide PCCs in screening for OUD and common comorbid conditions, including depression and anxiety. Opioid Wizard includes an EHR-based tool that calculates risk of opioid overdose or OUD and alerts PCCs to patients at increased risk. It also algorithmically identifies and alerts PCCs to patients with OUD diagnoses or a history of opioid overdose.

In both intervention and control clinics, suicide risk scores will be calculated for all Opioid Wizard-eligible patients (at high risk of OUD/overdose or diagnosed with OUD) and archive relevant EHR data to inform analyses. In intervention clinics, Opioid Wizard will alert PCCs to Opioid Wizard-eligible patients who are at increased risk of suicide and coach them through use of the Columbia Suicide Severity Risk Scale (CSSRS), a structured tool in the EHR that will help PCCs assess immediate suicide risk. Based on the resulting CSSRS score, Opioid Wizard will provide EHR links for risk-based referrals and follow-up recommendations, including care as usual, routine or

emergent referral to behavioral health, or transportation to the emergency department for further assessment.

**Specific Aims:**

**Aim 1. Evaluate the impact of Opioid Wizard + Suicide Risk Prediction on suicide assessment process measures.**

**H1:** Opioid Wizard-eligible patients (patients with OUD or at elevated risk of OUD/overdose) with elevated suicide risk in intervention clinics will have higher rates of completed CSSRS assessments than similar patients in control clinics.

**Aim 2. Examine the impact of Opioid Wizard + Suicide Risk Prediction on patient engagement in mental health care.**

**H2:** Opioid Wizard-eligible patients with elevated suicide risk in intervention clinics will have higher rates of engagement in their outpatient mental health care than similar patients in control clinics.

**E. Study Design**

**1. Overview of Study Design.** When a patient is at elevated risk of suicide, the PCC will be prompted by Opioid Wizard to complete the CSSRS, easily available to all PCCs in the EHR and saved as discrete data elements. Risk-based (depending on CSSRS score) referral and follow-up recommendations for suicide prevention will be given, with specific care recommendations ranging from care as usual (very low risk) to referral to behavioral health for evaluation and safety planning (moderate to high risk) to immediate evaluation in the emergency department and potential inpatient admission (very high risk), building on workflows developed for use by care managers in our recently completed suicide prevention trial of over 19,000 people at elevated risk of suicide.

The MHRN suicide risk models will be programmed into the EHR, a rigorous process that will take approximately 6 months. This process includes building the model in a testing environment in the EHR, testing the model with fictitious patients in a EHR testing environment and conducting chart audits, revising as needed, testing the model in a different EHR testing environment with real patient data, revising as needed, testing the model by running it silently in the EHR production environment and conducting chart audits, and revising as needed. This is followed by testing in the EHR production environment with 5-15 physicians in 1-2 pilot clinics. Prior to the go-live date for the suicide risk calculator, training on use and interpretation of the suicide risk model and the CSSRS will be provided to all PCCs and their rooming staff in intervention clinics. Training for control clinics will be separate and will provide training on the use of the CSSRS.

**2. Duration of Study and Visit Schedule.** In the parent trial, HealthPartners primary care clinics (n=30) will be randomized to receive or not receive access to the OUD-CDS. In this supplemental study, the clinics receiving access to the OUD-CDS (n=15) will be further randomized (1:1) to receive or not receive access to the MHRN suicide risk models and associated CDS. PCCs in HealthPartners clinics with CDS access will have access to the main OUD-CDS intervention for up to 30 months from date of implementation. PCCs in HealthPartners clinics randomized to the suicide model intervention will have access to the suicide supplement intervention for up to 12 months from date of implementation.

In Suicide Supplement control clinics, the OUD-CDS will run silently in the background over the same time periods, collecting data without displaying. There is no study-determined visit schedule; rather, patient visits will be jointly determined by the patient and PCC. Having the OUD-CDS run from implementation through the end of the observation period in all randomized clinics in each health care system ensures that identical methods are used to identify study-eligible patients and track patterns of OUD-related care so that we may quantify the impact of the OUD-CDS on OUD identification and care.

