## F. Study Population

**1. Primary Care Clinics:** For this supplemental study, study clinics will include all 15 HealthPartners primary care clinics randomized to the intervention in the parent study (COMPUTE 2.0); half of these clinics will be randomized to receive access to the suicide risk models and alerts, and half will not. Each primary care clinic has at least 3 eligible PCCs and 50 adult patients who meet inclusion criteria for the parent study (see Section C.6 in the COMPUTE 2.0 Protocol).

**2. Primary Care Clinicians (PCC):** To be eligible for inclusion in the parent study (and therefore also this supplemental study), a PCC must practice at least 0.5 full-time equivalent at a study-eligible primary care clinic and be a family physician, general internist or adult-care non-obstetric nurse practitioner or physician assistant. PCCs are study-eligible regardless of whether they are waivered to prescribe buprenorphine. PCCs in the intervention clinics will be encouraged but not required to use Opioid Wizard with eligible patients; the decision to use or not use the CDS at a given clinical encounter is up the PCC at each clinical encounter.

**Consent:** We will request a waiver of written informed consent from the IRB for PCCs for the intervention, because the CDS is based on current national standards of care and does not make treatment recommendations that are not accepted as community standards of care, and because consenting PCCs would compromise the external validity of the study by introducing selection effects. Our IRB has granted such waivers for similar studies, including the parent study.

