#### **N. Safety Reporting**

We do not anticipate that a Data and Safety Monitoring Board (DSMB) will monitor this study. We will report any unanticipated safety events to the HealthPartners IRB, as required. This study will randomize clinics to receive or not receive a CDS tool to facilitate the provision or accepted standards of care. With this work, we are not attempting to change the standard of care for OUD treatment or mental health treatment in primary care, but rather are attempting to help PCCs achieve this standard of care. PCCs will be trained that, as with other clinical decision tools, the

OUD-CDS and the suicide risk module are meant to supplement but not supersede clinical judgment. PCCs will be able to choose to follow or to not follow the guidance of the CDS at any given time for any given patient. PCCs will be asked to use the Feedback Tab within the tool to let the team know of questions, potential errors, or when their clinical judgment is inconsistent with the CDS. This feedback will be monitored by the treatment team and the CDS algorithms adjusted if indicated.

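### Section E.2 contradicts itself on whether supplement control clinics see the OUD-CDS, and Sections F.3 and I give different index-visit rules

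*Combined protocol and SAP*

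**What the plan says.** **Display in control clinics.** Section E.2 first describes a two-stage design within HealthPartners: "the clinics receiving access to the OUD-CDS (n=15) will be further randomized (1:1) to receive or not receive access to the MHRN suicide risk models". Clinicians in clinics with CDS access "will have access to the main OUD-CDS intervention for up to 30 months from date of implementation", and those randomized to the suicide supplement have that component for up to 12 months. Section F.1 agrees that all 15 clinics are parent-trial intervention clinics and that "half of these clinics will be randomized to receive access to the suicide risk models and alerts, and half will not". Sections G.2 and I also vary only the suicide component.

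The next paragraph of E.2 then says: "In Suicide Supplement control clinics, the OUD-CDS will run silently in the background over the same time periods, collecting data without displaying". It explains that running the tool "in all randomized clinics in each health care system" allows identical case-finding "so that we may quantify the impact of the OUD-CDS on OUD identification and care".

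**Index visit.** Section F.3 defines the index visit as the first at which every eligibility criterion is met, including criterion (c), high risk on the suicide models, and attributes the patient to the clinic of that visit. Section I attributes the patient to the clinic of the first visit eligible for the OUD-CDS intervention, calls that the index visit, and does not mention suicide risk. Section G.1 refers to the first visit at which the algorithms find the patient eligible for the intervention, without saying which intervention.

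**The concern.** These statements fix what the control arm receives, which arm a patient belongs to, and when the outcomes are measured.

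*Comparator.* If the OUD-CDS is hidden in control clinics, the trial compares OUD-CDS plus suicide module with nothing displayed. Section D says the OUD-CDS itself guides screening for depression and anxiety. H2 (Section J.1) counts primary care visits carrying a mental health diagnosis or made with a behavioral health clinician. The OUD-CDS alone could move that outcome, so the module's effect could not be separated out.

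*Index visit.* H1 is CSSRS assessment at the index visit, and H2 counts visits after it. The alert fires only once the algorithms flag the patient (Section F.3, definition of high risk). For a patient flagged later than the first OUD-CDS-eligible visit, the Section I rule scores H1 at a visit where the intervention could not act and starts the H2 count there. It may also assign another clinic's arm, since Section I itself allows later visits to fall in other clinics or treatment groups. Two live definitions also leave a choice that could be made after the data are seen.

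**Working it through.** This is mainly a check of text against text. Arithmetic serves only to show scale.

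**Step 1. Can the display statements be reconciled?**

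| Section | What a supplement control clinic has |
|---|---|
| E.2, first paragraph | OUD-CDS access; no suicide models or associated CDS |
| F.1 | A parent intervention clinic without the suicide models and alerts |
| G.2, I | Only the suicide component differs between arms |
| E.2, second paragraph | OUD-CDS runs but is not displayed |
| F.3, Table 1 | No EHR alerts; the kind of alert is not specified |

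The second paragraph of E.2 is the outlier, and Table 1 does not settle the matter. Taking OUD-CDS there to mean only the suicide module is difficult. The first paragraph of E.2 distinguishes the main OUD-CDS intervention from the supplement, and Section N names the two side by side: "OUD-CDS and the suicide risk module are meant to supplement but not supersede clinical judgment". The stated purpose of the silent running, the effect of the OUD-CDS on OUD care across health systems, is not a supplement hypothesis and does not suit a study confined to HealthPartners clinics. The paragraph looks carried over from the parent trial; that is an inference.

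**Step 2. Scale of the display issue, if applied literally.** A 7/8 split is assumed from Section I's roughly even allocation.

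- Clinics: 7/15 = 46.7%; 8/15 = 53.3%.
- Control patients in the 5% scenario: 125 × 7/15 = 58; 125 × 8/15 = 67.
- Control patients in the 20% scenario: 500 × 7/15 = 233; 500 × 8/15 = 267.

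The patient counts assume equal clinic sizes and the plan's one-year accrual figures.

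**Step 3. Are the two index-visit rules equivalent?** First, the plan's own figures in Section J.3 reproduce.

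- 4968 / 2 = 2484, close to the stated 2500. Halving is assumed, because 15 of the 30 clinics are used.
- 2500 × 5%, 10%, 20% = 125, 250, 500.
- Divided by 15 clinics: 8.3, 16.7, 33.3, matching the stated 8, 16 and 33 after truncation.

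Section J.3 therefore treats OUD-CDS-eligible patients as a wider group than supplement-eligible patients: 2500/500 = 5 and 2500/125 = 20, so 5 to 20 times as many. Per clinic, 2500/15 = 167 against 8 to 33. A visit can meet the Section I rule without meeting the Section F.3 rule.

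Two further figures point the same way, but more weakly.

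- The smallest clinic in J.3 has 66 OUD-CDS-eligible patients a year, and 66/33 = 2.0. This sets a minimum across all parent-eligible clinics against an average in the 20% scenario.
- Section F.1 requires at least "50 adult patients who meet inclusion criteria for the parent study" per clinic, and 15 × 50 = 750 > 500. No period is stated, and F.3 literally lists suicide risk among the parent criteria.

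**Step 4. Which index rule fits the rest?** Section G.2 defines the intervention as the suicide prevention CDS. Read with that, G.1 supports F.3. J.1 applies H1 to patients with elevated suicide risk assessed at the index visit, which also fits F.3. Section I is the outlier.

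**The case against.** The strongest reply is that OUD-CDS is used loosely throughout. Section B describes the suicide models as built into Opioid Wizard, Section H.1 collects supplement outcomes through the OUD-CDS, and the G.1 reading above needs the OUD-CDS algorithms to include the suicide models. On that view, the silent-running sentence, which directly follows the 12-month supplement sentence and is limited to supplement control clinics, simply means that the suicide component is silent. Section I would likewise be shorthand for F.3, which lists high suicide risk among the criteria for the parent study and hence the supplement.

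Part of this stands. The intended comparator can be recovered from the rest of the protocol, so the harm in Step 2 arises only on a literal reading. The index-visit conflict is less stark than the display conflict, and G.1 is ambiguous. The counts do not measure harm.

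The loose usage does not remove either problem, however. If OUD-CDS means the whole platform, hiding it still withholds the main component. If eligibility for the OUD-CDS means eligibility for any part of it, the first such visit can still precede the suicide flag. The separate naming in E.2 and the separate counts in J.3 weigh against the shorthand reading.

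**Conclusion.** Both points hold, and the text must be corrected before use. The display contradiction is direct: Section E.2 gives supplement control clinics the OUD-CDS in one paragraph and hides it in the next. The index-visit conflict is a difference between two stated rules that the plan's own numbers show are not equivalent.

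Applied literally, the display sentence affects 47% to 53% of clinics, holding roughly 58 to 267 supplement patients across the plan's scenarios. Those counts rest on a 7/8 split, equal clinic sizes (J.3 shows a range of 66 to 387 OUD-CDS-eligible patients per clinic) and a full year of accrual. Section F.3 allows only 9 months, which would lower them by a quarter under uniform accrual.

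For the index visit, the 5-to-20-fold ratio shows only that the definitions differ. How many patients are flagged after their first OUD-CDS-eligible visit, and how many would change arm, cannot be derived from the documents. No loss of power is claimed.

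**What to change.** 1. In the second paragraph of Section E.2, state that the suicide risk module is what runs without display in supplement control clinics, consistent with Sections D, F.1 and G.2 and the first paragraph of E.2. Reword the purpose sentence to refer to the supplement's question and to HealthPartners clinics.
2. In Section I, replace the index-visit wording with the Section F.3 definition, and use it for arm attribution, the H1 outcome and the start of H2 follow-up.
3. In Section G.1, name the intervention meant, so that it matches F.3.

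The cost is protocol wording only. Sample size, randomization and data collection are unchanged.

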## F. Study Population

**1. Primary Care Clinics:** For this supplemental study, study clinics will include all 15 HealthPartners primary care clinics randomized to the intervention in the parent study (COMPUTE 2.0); half of these clinics will be randomized to receive access to the suicide risk models and alerts, and half will not. Each primary care clinic has at least 3 eligible PCCs and 50 adult patients who meet inclusion criteria for the parent study (see Section C.6 in the COMPUTE 2.0 Protocol).

**2. Primary Care Clinicians (PCC):** To be eligible for inclusion in the parent study (and therefore also this supplemental study), a PCC must practice at least 0.5 full-time equivalent at a study-eligible primary care clinic and be a family physician, general internist or adult-care non-obstetric nurse practitioner or physician assistant. PCCs are study-eligible regardless of whether they are waivered to prescribe buprenorphine. PCCs in the intervention clinics will be encouraged but not required to use Opioid Wizard with eligible patients; the decision to use or not use the CDS at a given clinical encounter is up the PCC at each clinical encounter.

**Consent:** We will request a waiver of written informed consent from the IRB for PCCs for the intervention, because the CDS is based on current national standards of care and does not make treatment recommendations that are not accepted as community standards of care, and because consenting PCCs would compromise the external validity of the study by introducing selection effects. Our IRB has granted such waivers for similar studies, including the parent study.

**3. Patients:** To be eligible for inclusion in the parent study (and therefore also this supplemental study), a patient must: (a) be aged 18-75 years, inclusive; (b) have an OUD diagnosis, be prescribed an active MOUD, or be identified by the opioid risk models as being at high risk of OUD or overdose; and (c) be identified at high risk of suicide by the suicide risk models. There are no exclusions for pregnancy, lactation, or mental health or behavioral health diagnoses. The first visit at which all eligibility criteria are met will be the index visit. Patients who meet the following criteria at their index visit will be excluded and not be exposed to the intervention: (a) active parenteral chemotherapy within the last year; (b) stage 4 or equivalent cancer diagnoses; or (c) enrolled in hospice or palliative care programs. Patients will accrue in the first 9 months of the 12 month intervention period to allow for at least 3 months of data collection for every patient. All PCCs and eligible patients will be attributed to the clinic at which they practice (PCC) or their index visit took place (patients) and to the arm to which their clinic is randomly assigned.

**Consent:** We will request and anticipate receiving a waiver of written informed consent from the IRB for patient participation because the study is minimal or less than minimal risk

Table 1. Summary of Clinic Access & Training

| Suicide Supplement Intervention Clinics   | Suicide Supplement Control Clinics |
|---|------------------------------------|
| EHR alerts to patients at elevated risk of suicide per the MHRN suicide risk models                                   | No EHR alerts                      |
| EHR access to the CSSRS that includes risk-based referral and follow-up recommendations for care based on CSSRS score |                                    |
| Training on use of the CSSRS via live and recorded webinars and follow-up handouts                                    |                                    |

compared to the risk associated with any primary care encounter, and because the study could not practically be conducted if written informed consent were required to be obtained in the context of busy community-based primary care clinics. We have requested and received such waivers in several similar prior studies, including the parent study. Patients who have requested non-participation in research studies will be excluded from all analyses.

**Definition of High Risk:** Algorithms determine when a patient is identified as being at high risk for OUD or opioid overdose or for suicide attempts or deaths, and, in intervention clinics, this will trigger a best practice alert to be displayed for a particular patient at a particular clinic encounter. These algorithms are housed on a web platform that interacts with the EHR to pull data elements to run risk equations and determine patient eligibility. Separate risk models for OUD/overdose and suicide attempt/death will be used.

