### **J. Analysis**

#### **1. Study Hypotheses**

**H1:** Opioid Wizard-eligible patients (patients with OUD or at elevated risk of OUD/overdose) with elevated suicide risk in intervention clinics will have higher rates of completed CSSRS assessments than similar patients in control clinics.

**H2:** Opioid Wizard-eligible patients with elevated suicide risk in intervention clinics will have higher rates of engagement in their outpatient mental health care than similar patients in control clinics.

The hypotheses for this supplemental study predict that the Opioid Wizard + Suicide Risk Prediction intervention will increase (a) the likelihood that Opioid Wizard-eligible patients with elevated suicide risk are assessed at the index visit for immediate suicide risk using the CSSRS (H1); and (b) the rate of post-index primary care visits with a mental health diagnosis or with a behavioral health clinician (H2). These hypotheses will be tested using generalized linear mixed models so that each outcome may be estimated among intervention relative to control clinics while accounting for patient outcomes clustered within randomized clinics via a random clinic intercept. Both outcomes will likely be normalized with a Poisson-Normal link function, although the distribution of visits may warrant using a Negative Binomial-Normal link.

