## O. Study Timeline

The study timeline began on October 1, 2020. Trial preparation will include obtaining Institutional Review Board (IRB) approval, building and testing the Suicide Risk Models, and training clinicians. Active intervention and data collection will continue for 12 months, including at least 3 months follow-up per patient.

| Study Timeline   | Quarter | 2020-2021 |         |         |         | 2021-2022 |         |         |         |
|--|---------|-----------|---------|---------|---------|-----------|---------|---------|---------|
|  |         | Oct-Dec   | Jan-Mar | Apr-Jun | Jul-Sep | Oct-Dec   | Jan-Mar | Apr-Jun | Jul-Sep |
| Phase 1: Development, Testing, Training                           |         |           |         |         |         |           |         |         |         |
| Finalize protocol, obtain IRB approval                                   |         |           |         |         |         |           |         |         |         |
| Build, install and test the MHRN suicide risk calculator in the EHR      |         |           |         |         |         |           |         |         |         |
| Clinic trainings   |         |           |         |         |         |           |         |         |         |
| Phase 2: Active Intervention                                      |         |           |         |         |         |           |         |         |         |
| Go live & primary data collection  |         |           |         |         |         |           |         |         |         |
| Patient recruitment (allowing for $\geq 3$ months follow-up per patient) |         |           |         |         |         |           |         |         |         |
| Monitor use rates, provide clinic- and PCC-level use reports             |         |           |         |         |         |           |         |         |         |
| Update, troubleshoot algorithms as needed                                |         |           |         |         |         |           |         |         |         |
| Phase 3: Analysis and Reporting                                   |         |           |         |         |         |           |         |         |         |
| Preliminary reports of available data to funder                          |         |           |         |         |         |           |         |         |         |

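### The 9-month accrual limit is applied to H1, which needs no follow-up, so H1 drops usable patients first flagged in months 10 to 12 from both arms

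*Combined protocol and SAP*

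**What the plan says.** - **Accrual (F.3).** "Patients will accrue in the first 9 months of the 12 month intervention period". The only reason given is "to allow for at least 3 months of data collection for every patient".
- **Module access (E.2).** Clinicians in intervention clinics "will have access to the suicide supplement intervention for up to 12 months from date of implementation".
- **Alert trigger (F, Definition of High Risk).** When the algorithms flag a patient in an intervention clinic, "this will trigger a best practice alert to be displayed for a particular patient at a particular clinic encounter". No section switches alerts off for newly flagged patients after month 9.
- **Data capture.** Section D has suicide risk scores calculated and EHR data archived in both arms. Section E.2 has the CDS running in all randomized clinics to the end of observation. Section O says "Active intervention and data collection will continue for 12 months, including at least 3 months follow-up per patient".
- **Outcomes (J.1).** H1 is the likelihood that eligible patients "are assessed at the index visit for immediate suicide risk using the CSSRS (H1"). H2 is a rate of visits after the index visit.
- **Sample size (J.3).** Patients are counted over one year of accrual: 125, 250 or 500, entered as 8, 16 or 33 per clinic in 15 clinics.

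**The concern.** A rule that exists to guarantee follow-up is applied to an outcome that has none. A patient first flagged in month 10, 11 or 12 has an index visit, an arm and a known H1 result, yet does not enter the H1 analysis. In intervention clinics that patient can also receive the alert and the CSSRS prompt.

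Two things are at stake. The first is precision for H1, the aim with less power to spare: J.3 gives detectable screening rates of 14.2% to 65.0% against 3% in control clinics. With clinics fixed at 15, patients per clinic are the main quantity left to increase. The second is coverage: some patients exposed to the module are outside every planned outcome comparison.

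**Working it through.** **1. The plan's counts.** 2500 × 5%, 10%, 20% = 125, 250, 500. Divided by 15 clinics, this is 8.3, 16.7, 33.3, which matches the stated 8, 16, 33 after truncation. These are 12-month counts.

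**2. Share of first flags in months 10 to 12.** The documents give no timing, so two assumptions bracket it.

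*Even entry:* 3/12 = 25%. That loses 31, 63 or 125 patients and leaves 94, 188 or 375 (6.25, 12.5 or 25 per clinic).

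*Early entry:* if a standing panel makes visits at random at L per year, and a patient enters at the first one, the share is (exp(−0.75L) − exp(−L)) / (1 − exp(−L)). L = 2, 3, 4 is my assumption. J.3 uses the same values, but as control-arm rates for the H2 outcome.

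| L per year | Share lost | Of 125 / 250 / 500 |
|---|---|---|
| 2 | 10.2% | 13 / 25 / 51 |
| 3 | 5.9% | 7 / 15 / 29 |
| 4 | 3.2% | 4 / 8 / 16 |

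**3. Precision after clustering.** With the number of clinics fixed, variance is proportional to (1 + (m − 1) × ICC) / m, where m is patients per clinic. Moving from the 9-month to the 12-month set under even entry, the two extremes over J.3's scenarios are:
- 500 patients, ICC 0.05, m from 25 to 33.3: 0.0880 to 0.0785, a fall of 11% in variance (about 6% in standard error).
- 125 patients, ICC 0.01, m from 6.25 to 8.33: 0.1684 to 0.1288, a fall of 24% in variance (about 13% in standard error).

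The same formula with the early-entry shares gives a fall of about 1% (500 patients, ICC 0.05, L = 4) to 9% (125 patients, ICC 0.01, L = 2).

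**4. Detectable rate.** Solve ln(p/0.03) = (1.960 + 0.842) × √{[(1 − p)/p + 0.97/0.03] / n}, with n = 7.5m / (1 + (m − 1) × ICC) per arm, control rate 3%, power 0.80 and two-sided α 0.05.

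| Scenario | All 12 months | 10% lost | 25% lost |
|---|---|---|---|
| ICC 0.01, 33 per clinic | 11.0% | 11.5% | 12.6% |
| ICC 0.05, 8 per clinic | 35.0% | 38.1% | 44.9% |

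This formula does not reproduce J.3's 14.2% and 65.0%, so only the change along each row should be read. A pooled two-proportion formula moves less: for a 25% loss, from 10.1% to 11.3% and from 22.6% to 25.8%.

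**5. Direction.** The month-9 cut is by calendar and applies to both arms alike, so it does not by itself bias the comparison.

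**The case against.** **The window is a reasoned choice.** It gives every patient a minimum of data, and one cohort gives H1, H2 and the event outcomes a common denominator. That stands as a reason for the 9-month limit on H2. It is weak for H1, which has no follow-up to protect.

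**The loss may be small.** Eligible patients are largely an existing panel, so many first visits may come early and the loss may be nearer 3% than 25%. Counting patients also overstates the gain, because clustering dilutes it. Both points stand and are reflected in the range.

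**A reader might infer that late-flagged patients have no safety data.** The documents do not support this. F.3 limits who accrues, not what is captured. Scoring, archiving and CDS data collection carry no month-9 limit (D, E.2), outcomes come from CDS data and EHR pulls (H.1), and collection lasts 12 months (O). Clinician reports through the Feedback Tab or email (H.4) and reports to the IRB (N) are not restricted to accrued patients. Nor does the plan define a safety set from which anyone is excluded; effects on attempts and overdoses are exploratory (J.4).

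**A reader might also infer that the data pull can run past month 12 because the main tool is available longer.** E.2 gives clinics the "main OUD-CDS intervention for up to 30 months from date of implementation", but that clock starts when the main tool goes live. The documents do not show how much of it remains when the supplement ends, so feasibility is not established.

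**Conclusion.** The point holds as a question of efficiency and coverage. H1 gives up patients whose outcome is already known and recorded, and the H1 population does not match the one-year count in J.3. The loss is 25% under even entry and about 3% to 10% under early entry at 2 to 4 visits a year. Including these patients would lower the H1 variance by about 11% to 24% under even entry, and by less under early entry. No bias in H1 follows from the cut alone.

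The patients concerned remain covered by EHR capture, clinician feedback and IRB reporting. What they lack is a place in the planned outcome analysis, and their follow-up within the 12 months would be under 3 months.

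This rests on two readings. First, H1 is measured at the index visit, as J.1 states; H.1 lists frequency of CSSRS completion without a time limit. Second, alerts continue for newly flagged patients to month 12, since no section says otherwise. It is a cheap improvement rather than a flaw that threatens the trial.

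**What to change.** - **H1 population (F.3 and J.1).** Define it as all patients whose index visit falls in months 1 to 12. Keep the 9-month limit for H2.
- **Late-flagged patients.** Report suicide attempts, overdoses, and ED or inpatient encounters for patients first flagged in months 10 to 12, descriptively by arm, to month 12 and with person-time. This stays within the collection period in Section O.
- **J.3.** State which accrual window each aim's patient count refers to: 12 months for H1, 9 months for H2.
- **Sensitivity analysis.** Show H1 in the 9-month cohort as well.

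The cost is a few sentences in the protocol and a wider date range for the H1 dataset, drawn from data already captured. The downside is that H1 and H2 have different denominators, which the plan and the report should state; the sensitivity analysis gives H1 on the H2 cohort.
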